5 STUDY POPULATION

PARTICIPANTS:

Inclusion/Exclusion criteria:

Inclusion: Treatment-seeking men and women between 18 and 65 years of age, with OUD confirmed by history and physical including urine toxicology, medical records and self-report, and interested in injectable extended-release agonist or antagonist treatment. Eligible candidates may have concurrent non-opioid substance use disorders, but opioids must be their drug of choice. Mild to moderate Depressive and Anxiety disorders and Attention Deficit Hyperactivity Disorder that do not require prescription stimulants and DSM Cluster B and C personality disorders are also included. Participants must have a stable address, working command of the English language, and telephone access. **Exclusion:** (1) Major current DSM V psychiatric disorders except those listed in the inclusion criteria and lifetime history of psychotic disorders (American Psychiatric Association 2013); (2) Medical and surgical conditions such as a malignancy that may affect patients' ability to receive XRNTX or XRBUP treatment because it may interfere with opioid analgesia; (3) Women of child-bearing potential who are pregnant or contemplating pregnancy in the next 6 months, nursing or not using an effective contraception.

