Biochemical Assessments:

Urine Toxicology: Rapid semi-quantitative ELISA urine drug screen test for morphine, oxycontin, methadone, buprenorphine, fentanyl, cocaine, amphetamine, methamphetamine, benzodiazepines, PCP and THC. Urine sample collection procedure has been described in a recent paper (Wang et al 2015).

Neuroimaging and cognitive: Overview of BOLD fMRI paradigms design: BOLD fMRI is a relative (non-absolute) measure, and experimental results are typically reported as contrast between conditions. Two main strategies are event-related and block designs (Aguirre et al 1999, Laurienti et al 2003).

Resting-state fMRI (rs-fMRI): During the 5-min rs-fMRI, participants will be instructed to stay awake, still, and to keep their eyes open. A fixation crosshair will be shown on a black background throughout the scan. No task performance will be required.

Visual Opioid Cue Task: Forty-eight drug-related and 48 control stimuli are presented randomly for 500 msec, separated by variable inter-trial intervals (ITI, 0–18 s). The stimuli sets are tailored to a specific pattern of OUD: prescription opioids only, heroin (IV and IN) only, and mixed prescription opioids and heroin (Shi 2016). The control stimuli that depict household objects and

chores are graphically and contextually matched to the drug-related stimuli (Langleben et al 2008, Wang et al 2015). Opiate craving is assessed with a subjective craving score (SCS), before and after each MRI session on a 0–9 Likert scale. There is no response requirement in the task, avoiding the possible confounds of individual differences in motor coordination/reaction time.

fMRI Go-NoGo task (GNG): The Go-NoGo fMRI task is a validated task testing cognitive control aspect of executive functions adopted from previous research (Goldman et al 2015). The Go stimuli included 122 positively valanced pictures (e.g. sweets), and the No-go stimuli were 38 negatively valanced pictures (e.g. snakes). Each trial consisted of a stimulus displayed for 300 ms, followed by 1700-ms baseline period during which a crosshair was displayed. Pseudo-random order of the stimuli and baseline periods was generated. Total Task Time: ~8 min. Our preliminary task performance data indicate that Go-NoGo task performance predicted XRNTX treatment failure ($p<0.01$). Performance will be coded by the number of errors of commission.

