Hamilton Depression Rating Scale (HAM-D) (Hamilton 1959). The HAM-D is a 20-minute, 24-item interview that measures the severity of depression and changes in depressive symptoms.

Clinical Opiate Withdrawal Scale (COWS) (Wesson et al 2003). The COWS is a clinician-administered instrument that measures eleven common opioid withdrawal symptoms.

Short Form-McGill Pain Questionnaire-2 (SF-MPQ-2) (Dworkin et al 2015) (PhenX #190901) is a 22-item self-administered questionnaire that asks about the different qualities of pain and related symptoms. Respondents are asked to rate the intensity of each type of pain they felt during the past week on a scale from 0 to 10

Timeline Follow-Back Interview (TLFB) (Sobell et al 1992). The TLFB is a 15-30-minute, semi-structured interview designed to measure self-reported drug use. It will be used at baseline to capture all drug use in the past 30 days including prescribed concomitant medications (PhenX 27016266).

Weekly online self-reported TLFB is a modified TLFB interview that uses a calendar-based format to record participants' self-report of past week drug use.

Experimental Assessments:

Urine Toxicology: Rapid semi-quantitative ELISA urine drug screen test for morphine, oxycontin, methadone, buprenorphine, fentanyl, cocaine, amphetamine, methamphetamine, benzodiazepines, PCP and THC. (Urine sample collection procedure has been described in a recent paper (Wang et al 2015).

Neuroimaging and cognitive: Overview of BOLD fMRI paradigms design: BOLD fMRI is a relative (non-absolute) measure, and experimental results are typically reported as contrast between conditions. Two main strategies are event-related and block designs (Aguirre et al 1999, Laurienti et al 2003).

Resting-state fMRI (rs-fMRI): During the 5-min rs-fMRI, participants will be instructed to stay awake, still, and to keep their eyes open. A fixation crosshair will be shown on a black background throughout the scan. No task performance will be required.

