Analyses of effects of neural response on relapse vulnerability: We consider the effect for an individual neural change variable, in a model where Group is included, assuming a small effect for Group (odds ratio = 1.25). We have three domains, with two neural variables in two domains and one in the other, so we provide power for $\alpha=0.05$ and for $\alpha=0.025$. For $\alpha=0.05$ we have 80% power for an odds ratio of 1.75 or higher per standard deviation increase in a neural variable; for $\alpha=0.025$, we have 80% for an odds ratio of 1.86 or higher.

Analyses of polysubstance use outcomes: We will also examine the effects of Group and neural change variables on other substance use outcomes, including self-report and UDS measures of opioid, stimulant, and benzodiazepine use. Here, we will use the self-report and UDS measures to create binary weekly measures of use for each substance, and use GEE repeated measures logistic regression models, with Group and the neural change measures as predictors, to estimate and test effects. These secondary analyses will be subject to missing data. We anticipate 25% dropout rates. To assess possible effects of nonignorable missingness on inference, we will perform sensitivity analyses using pattern-mixture models and selection models. For pattern mixture models, subjects are grouped on the basis of their pattern of missing data, and the resulting categorical factor is included in the analyses as a main effect and interaction with predictors of interest. Overall predictor effects may be found by averaging over the patterns (Molenberghs et al 2005). Selection models (Molenberghs et al 2005) take a different approach, by explicitly modeling the probability of drop out, and incorporating the predicted probabilities into the main longitudinal analysis, with the dropout and response processes included in a single bivariate model. Comparisons between the predictions of the primary analyses, and each set of pattern mixture and selection models, provides some evidence for assessing the sensitivity of results to missing data.

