9.4 Statistical Analyses

9.4.1 General Approach

Data Management. Data will be gathered using Penn's REDcap data collection system, a direct-entry data system where subjects can directly enter responses. REDcap is HIPAA compliant and data is secured on Penn Medicine's data management unit (DMU) network. Interview data and self-report data are entered directly into REDcap at the research sites, by research technicians and study subjects respectively. Field validation (eg, no out of range or otherwise invalid responses will be accepted) and form validation (e.g. logically impossible responses to different questions will not be accepted) are built into this entry process. Data are transmitted (128-bit encrypted form) over the internet to the DMU servers. After online reviews, the data are archived on the servers. Certain DMU staff members have permission to modify the archived data. Audit logs record any modification to the original entry. Password protection allows members of the research team appropriate levels of data access. At time of data collection clinical research staff will review data collected for completeness (field and form validation). Weekly routine data inspections will be performed by clinical research staff to ensure data integrity. Subject brain scan data are extracted via CAMRIS web-servers and are archived to lab-specific, encrypted servers for standard cleaning and analysis.

Data Analyses. [name], the CSA Statistician, and his staff will perform the data analyses. Prior to analyses, standard data screening/cleaning procedures will be applied ⁵³. These procedures will screen the data for data-entry errors, check for outliers, assess the extent and pattern of missing data, and check that appropriate assumptions of normality are met whenever necessary. Due to sample size, it is unlikely that the randomization will result in significant imbalance of the distributions of demographic or other variables across treatment groups. Additional covariates will be considered for inclusion in the analyses, to improve the precision of estimation for the treatment effects. Covariates describing levels of cocaine use prior to the study may be included. Assumptions underlying the application of statistical methods will be examined, through use of standardized residuals, influence diagnostics, and graphical displays.

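### The secondary weekly stimulant and benzodiazepine models do not pre-specify baseline use of the same substance, although the trial already records it

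*Combined protocol and SAP*

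**What the plan says.** Section 9.1 (Analyses of polysubstance use outcomes) covers "other substance use outcomes, including self-report and UDS measures of opioid, stimulant, and benzodiazepine use". It will "create binary weekly measures of use for each substance" and then "use GEE repeated measures logistic regression models, with Group and the neural change measures as predictors, to estimate and test effects". No baseline term is listed.

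Two sentences in section 9.4.1 (Data Analyses) bear on covariates. The first is general: "Additional covariates will be considered for inclusion in the analyses, to improve the precision of estimation for the treatment effects". The second names one example: "Covariates describing levels of cocaine use prior to the study may be included". Neither refers to the polysubstance models.

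The information exists. Of the TLFB, section 8 says: "It will be used at baseline to capture all drug use in the past 30 days including prescribed concomitant medications". The UDS panel in section 6.1 includes "fentanyl, cocaine, amphetamine, methamphetamine, benzodiazepines, PCP and THC". The Schedule of Activities appears to mark both at screening and at day 0. Section 5 states: "Eligible candidates may have concurrent non-opioid substance use disorders". Section 6.3 stratifies randomisation on sex only.

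**The concern.** For a weekly measure of cocaine, amphetamine or benzodiazepine use, earlier use of the same drug is the baseline value of the outcome and would ordinarily be expected to predict it strongly. This trial admits people with other substance use disorders and detoxifies them from opioids. Section 2.2.1 acknowledges that the study drugs do not prevent non-opioid use. Much of the between-person variation in these outcomes may therefore be present before randomisation, and the design does not balance it.

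Two things are at stake.

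- **Group.** A prognostic baseline left out of the model makes the randomised comparison less precise.
- **Neural change.** This predictor is not randomised. If the size of a person's PRE-to-ON change is related to prior stimulant or benzodiazepine use, an unadjusted model can report a link between brain response and use that only reflects who was already using.

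Leaving the covariate optional also lets the choice be made after results are seen.

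**Working it through.** **No figure to reproduce.** The documents give no power statement, use rate or effect size for these models. The size of the problem has to be simulated over assumed ranges.

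**Inputs from the documents.**
- Analysis sample 140, i.e. 70 per group (9.1). Section 9.2 says 80 per group; 70 is used here.
- Anticipated dropout 25% (9.1): 140 × 0.75 = 105.
- A 12-week medication phase (3.1), taken as 12 weekly binary results.

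**Models compared**, for person i in week t:
- A (as written): logit P(use) = b0 + b1·Group + b2·NeuralChange
- B (with baseline): model A + b3·BaselineUse

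Both are logistic GEE-type fits with robust standard errors and two-sided 5% tests.

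**Assumptions not in the documents.**
- Set 1: baseline use in 30% or 50%; weekly use in baseline users vs non-users of 40% vs 20%, 50% vs 15% or 60% vs 10%; random-intercept SD 1.0; Group odds ratio 0.5; N=140; 1,500 trials per setting.
- Set 2: baseline use in 30% or 50%; odds ratio for baseline use 5 or 20; random-intercept SD 1.5; Group odds ratio 0.4; N=140 and 105; 3,000 trials per setting.
- Small effect: set 1 at 30% baseline use, with Group odds ratio 0.8. This is 1/1.25, and 1.25 is the odds ratio that 9.1 calls small in the treatment-success model.

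**Group power, model A vs model B.**

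| Setting | Without baseline use | With baseline use | Gain (points) |
|---|---|---|---|
| Set 1, 30%: 40/20, 50/15, 60/10 | 85, 70, 49% | 89, 85, 81% | 4, 15, 32 |
| Set 1, 50%: same order | 84, 75, 55% | 89, 89, 86% | 5, 14, 31 |
| Set 2, N=140, 30%: OR 5, 20 | 70, 52% | 76, 77% | 6, 25 |
| Set 2, N=140, 50%: OR 5, 20 | 74, 57% | 80, 80% | 6, 23 |
| Set 2, N=105, 30%: OR 5, 20 | 57, 41% | 64, 65% | 7, 24 |
| Set 2, N=105, 50%: OR 5, 20 | 61, 47% | 68, 69% | 7, 22 |
| Group OR 0.8, 30%: 40/20, 50/15, 60/10 | 17, 13, 9% | 19, 18, 15% | 2, 5, 6 |

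Gains are differences of the rounded percentages shown.

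**False-positive rate for neural change** when its true effect is zero (N=140), by its correlation r with baseline use:

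| r | Model A | Model B |
|---|---|---|
| 0 | about 5% | about 5% |
| 0.1 | 8-17% (set 2 alone: 8-13%) | 5-7% |
| 0.2 | 14-45% (set 2 alone: 16-37%) | 5-7% |
| 0.3 | 28-79% (set 2 alone: 30-69%) | 5-7% |

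**A separate check on the Group coefficient.** Neural change uses the ON scan, which the Schedule of Activities places at day 55, after injections at days 10 and 40. In models A and B alike, b1 is adjusted for a post-randomisation variable, so it is not the total effect of assignment to one drug rather than the other. Adding baseline use does not repair this.

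**The case against.** Several counter-arguments have force.

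- **The plan does not exclude the covariate.** A reader might infer from 9.1 alone that baseline use is ruled out. It is not: 9.4.1 contains a general provision for precision covariates that is not limited to cocaine. The supportable statement is that baseline use is optional and not pre-specified.
- **The large power gains rest on large Group effects.** Section 2.2.1 gives little reason to expect them on non-opioid use. At odds ratio 0.8 the gain is a few points, and power is below 20% with or without the covariate.
- **The neural-change problem is conditional.** A reader might infer that reported brain-use associations will be spurious. That needs a correlation between prior use and PRE-to-ON change, and the documents give none. At r=0 there is no inflation. The correlation cannot be assumed to be zero either, because neural change is not randomised.
- **Group is not confounded.** Randomisation protects it from systematic bias by baseline use; the loss is precision.
- **The outcomes are secondary.** Section 9.1 says so, and 2.2.1 calls concurrent non-opioid use exploratory.

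All five limit the size and reach of the point. None supplies a commitment. Neither sentence in 9.4.1 is tied to these models, and neither names benzodiazepines or stimulants other than cocaine. The plan's own reasoning points the same way: 9.1 orders model entry to separate Group from change scores in the treatment-success analysis, and expects clinical and neural predictors to overlap in the predictive modelling.

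**Conclusion.** The point holds as a gap in pre-specification in secondary analyses. The stimulant and benzodiazepine models are stated with Group and neural change only, and the baseline value of the outcome is left to discretion although it is collected.

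The cost for Group is precision: about 2 to 6 power points for a small effect, and 25 to 32 points at the extreme of a large effect with strongly persistent use. For neural change, the unadjusted false-positive rate rises from about 5% at r=0 to 8-17% at r=0.1, 14-45% at r=0.2 and 28-79% at r=0.3. With adjustment it stays near 5-7%. All these figures depend on assumed use rates, effect sizes and correlations. They show direction and plausible range and are not estimates for this trial.

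The documents do not support reading this as a threat to the primary fMRI interaction, the Phase 2 milestone or the treatment-success model. None of these uses the polysubstance models.

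**What to change.** In 9.1, state that each stimulant and benzodiazepine model includes one fixed covariate for pre-detoxification use of that same substance: TLFB days used in the past 30. Name the screening UDS result as the alternative in a sensitivity analysis rather than as a second, overlapping term. Replace the optional cocaine sentence in 9.4.1 with this rule.

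Two details need wording.

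- **Benzodiazepines.** Take the measure from before detoxification, because section 6.1 lists as-needed clonazepam during detoxification and this can make the day 0 screen positive. Exclude prescribed days if the TLFB record allows it. The documents say prescribed medication is captured, but not that it is recorded separately, so this should be checked first.
- **Group effect.** Report it from the model with Group and baseline use but without neural change. Use the model with neural change only for the neural association.

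The cost is one extra term per model and a text change, using data already collected. The Group odds ratio then becomes conditional on prior use, which the report should say.

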Predictive modeling: The models for relapse/treatment-success addressed the effects of neural responses, in isolation from demographic and clinical measures. In further analyses, we will examine their effects in combination with demographic and non-imaging clinical predictors. As we can expect overlap between the effects of these sets of variables, we compare the effects of these domains on prediction of treatment success. Thus, we will compare models using various sets of predictors on the basis of AUC comparisons, rather than on goodness of fit (Sullivan Pepe 2003). In our model search, we will compare models containing interactions between Group and the various predictors, with the constraint that an interaction is included only in models where the corresponding main effects are also included. First, we will find the best fitting demographic model, searching over a set including age, race, gender, and educational status. Next, with the predictors from the best demographic model included, we will search over the clinical predictors (depression and anxiety scores, measures of withdrawal and craving, and the ASI composite scores) to find the set that most improves the predictive utility of the best demographic model. Third, with the predictors from the best demographic/clinical model included, we will search over the measures of neural change to find the set that most improves the fit of the best demographic/clinical model. We will then perform goodness of fit and ROC comparisons between the best demographic, demographic/clinical, and demographic/clinical/brain models. This process involves three searches over various sets of variables, and unconstrained searches are likely to yield complex models involving many predictors, resulting in a prediction rule that performs poorly in new samples. To avoid this, we will use a lasso approach to fitting the logistic regression models for this hypothesis. The usual algorithms for logistic regression estimate the model parameters by minimizing a measure of lack of fit of the model to the data, but do not penalize models for complexity. The lasso approach selects a best fitting model subject to the constraint that the sum of the magnitudes of the regression coefficients in the model is less than a small positive threshold value. The threshold is chosen adaptively from the data, by minimizing an estimate of the prediction error for the model, using ten-fold cross validation. Then, a best fitting model is chosen with the estimated threshold used in the penalty. The best fitting model is usually one in which a number of the coefficients are set to zero, i.e. a number of predictors are dropped from the model.

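### The lasso described for the predictive models has no mechanism to guarantee the plan's own two rules: interactions only with their main effects, and earlier-stage predictors kept in

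*Combined protocol and SAP*

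**What the plan says.** The Predictive modeling paragraph of section 9.1 describes a three-stage search: demographic variables, then clinical variables, then measures of neural change. It lays down two structural rules.

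- Hierarchy: models with Group interactions are considered "with the constraint that an interaction is included only in models where the corresponding main effects are also included".
- Retention: at stage 2, "with the predictors from the best demographic model included, we will search over the clinical predictors". At stage 3, "with the predictors from the best demographic/clinical model included, we will search over the measures of neural change".

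To limit overfitting, the paragraph then states that "we will use a lasso approach to fitting the logistic regression models for this hypothesis". It defines the lasso as choosing the best-fitting model such that "the sum of the magnitudes of the regression coefficients in the model is less than a small positive threshold value". The threshold is set "by minimizing an estimate of the prediction error for the model, using ten-fold cross validation". The result is described as a model in which "a number of the coefficients are set to zero, i.e. a number of predictors are dropped from the model".

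The three resulting models are compared by goodness of fit and by ROC. H2b, labelled exploratory in sections 3.2 and 9.4.1, words the contrast as demographic plus clinical measures against the same set with brain response added.

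**The concern.** The rules say which terms must be in a model. The fitting method decides for itself which terms stay. Nothing in the documents says how the two are combined: no hierarchical or group penalty, no term exempt from the penalty, and no refit after selection.

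Two things are at stake. First, an interaction kept without its main effect changes meaning with the coding of Group. Suppose the term Group × x has coefficient δ and x has no main effect. With Group coded 0/1, the effect of x is 0 in one arm and δ in the other. With Group coded −1/+1, it is −δ in one arm and +δ in the other.

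Second, H2b asks what brain response adds to a demographic and clinical base. If that base loses predictors, or is shrunk differently, when the neural measures enter, the difference between the two models mixes the brain contribution with a change in the base. Group is also exposed. In the H2a analysis of section 9.1 the plan enters Group first, because it expects Group and the neural change scores to be confounded. A lasso that may shrink or drop Group does not carry that protection into the predictive models.

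**Working it through.** The plan gives no figure for this analysis, so there is nothing to reproduce. The check has two parts.

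**1. Form of the penalty.** Write γ for Group, β_k for main effects and δ_k for Group interactions. The method described maximises the log-likelihood subject to

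|γ| + Σ|β_k| + Σ|δ_k| ≤ t.

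With λ the multiplier for t, a coefficient is zero when the absolute score for its own term is below λ. The condition for δ_k does not refer to β_k or γ, so δ_k ≠ 0 with β_k = 0 or γ = 0 is an admissible solution. A predictor carried from an earlier stage sits in the same sum, faces the same test, and can be set to zero or shrunk by a new λ when candidates are added. Neither rule is encoded. This step needs no simulation.

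**2. How often it could matter.** A three-stage plain logistic lasso was simulated, with ten-fold cross-validation at minimum deviance and each stage carrying forward the variables selected before.

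Inputs from the documents:
- four named demographic candidates (section 9.1, Predictive modeling)
- five neural variables: three domains, two of them with two variables and one with one (section 9.1)
- n = 140 (section 9.1), with n = 200 also tried because Aim 2 in section 3.2 gives that figure
- a Group odds ratio of 1.25 (section 9.1), log-odds about 0.22

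Assumptions:
- 11 clinical candidates, since the plan names the types but not the count
- independent predictors
- success in about half of participants
- five true main effects of 0.35 or 0.50 log-odds per SD
- one true neural interaction of 0.35 or none

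If every variable were carried forward, the last stage would have 1 + 2 × (4 + 11 + 5) = 41 terms.

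| n, Group coding, main / interaction effect | Hierarchy broken | Same, ignoring absence of Group | Stage 2 dropped a demographic predictor | Stage 3 dropped an earlier predictor |
|---|---|---|---|---|
| 140, 0/1, 0.35 / 0.35 | 90% | 87% | 30% | 14% |
| 140, 0/1, 0.50 / 0 | 90% | 83% | 24% | 20% |
| 140, 0/1, 0.35 / 0 | 80% | 75% | 28% | 22% |
| 200, 0/1, 0.35 / 0.35 | 93% | 90% | 20% | 37% |
| 200, 0/1, 0.50 / 0 | 95% | 82% | 16% | 31% |
| 140, ±1, 0.35 / 0.35 | 86% | 80% | 23% | 17% |
| 140, ±1, 0.50 / 0 | 82.5% | 72.5% | 19% | 25% |

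There were 60 runs per 0/1 row and 80 per ±1 row. With 60 runs, the simulation standard error is at most √(0.5 × 0.5 / 60) = 6.5 percentage points. The last two columns are conditional on the earlier stage having selected something. They count a predictor as dropped only if both its main effect and its interaction left the model, so shrinkage alone is not counted.

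A separate single-fit simulation (not staged) assumed ten demographic and clinical predictors, a neural correlation of 0.3 and true odds ratios of 1.6 to 1.75. The hierarchy rule was broken in 65% of runs at 23% events, in 75% at 30% events, and in 25% with no true effect.

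**3. Does exempting terms from the penalty suffice?** The two ±1 rows were rerun with Group and the carried-forward main effects unpenalised. Dropped earlier predictors fell to 0%, by construction. The hierarchy rule was still broken in 47.5% and 37.5% of runs, through the newly searched variables.

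**The case against.** The best reply is that the paragraph gives a textbook account of the lasso, not an implementation. On that reading the two rules define the admissible models and the lasso operates only within them. This is possible, and it rules out a stronger inference a reader might draw: that a lasso cannot keep the hierarchy rule. Some fits obey it by chance, and hierarchical versions keep it by design. But the text describes one bound on all coefficients and predictors being dropped, and it does not describe a restricted search. Different ways of imposing the rules can select different models, so the choice belongs in the plan.

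A second reply is that AUC comparison does not require nested models, and the plan prefers AUC to goodness of fit for comparing predictor sets. That is correct, and the plan never uses the word nested. The same paragraph nevertheless goes on to plan goodness-of-fit comparisons, and reading the difference as the added value of brain response depends on the base staying in. A reader might also infer that the planned comparison is never nested. The simulations do not support that, since in most runs no earlier predictor was dropped.

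A third reply is that no confirmatory conclusion rests here, and this stands. Differences between medications in the effects of the neural scores are tested under H2a (section 9.1) by ordinary logistic regression, with interactions added to a model already holding Group and the neural main effects. H2b is exploratory, and section 10.2 expects that validation will need an independent sample.

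**Conclusion.** The point holds as a conflict between the plan's stated rules and its stated fitting method. The described lasso guarantees neither hierarchy nor retention, and no other section supplies the missing device. That conclusion follows from the form of the penalty alone.

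The size is less certain. Under the staged assumptions, hierarchy violations were common (80–95% of runs, or 72.5–90% ignoring the absence of Group). Loss of an earlier predictor was a minority event (16–30% at stage 2, 14–37% at stage 3). Raising n to 200 or recoding Group removed neither problem. The range of 25% to 75% in the single-fit simulation shows how far such figures move with the assumed effects and event rates. They are illustrative and do not predict this trial's result.

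A reader might infer that the trial's conclusions about differences between the medications are compromised. The documents do not support that: the H2a tests respect hierarchy, and the impact is confined to the exploratory H2b comparison. This is a minor but worthwhile correction.

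**What to change.** In the Predictive modeling paragraph of section 9.1:

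1. Replace the plain lasso with a hierarchy-respecting one (overlapping-group or strong-hierarchy), so that an interaction can be non-zero only when its main effects are in the model.
2. State that Group and the predictors carried forward are left unpenalised at later stages. This meets the retention rule. Both steps are needed: the second alone left the hierarchy rule broken in 37.5–47.5% of simulated runs, and the first alone does not force earlier predictors to stay.
3. State that the whole staged selection is repeated inside the cross-validation when AUCs are compared.

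The cost is a few sentences and a change of fitting routine, with no new data. The statistical price is less sparse models and some added overfitting risk, because predictors chosen from the same data are then kept without shrinkage. If failures ran at 23–30% (an assumption), 140 participants would give about 0.23 × 140 = 32 to 0.30 × 140 = 42 events, which is few for this many candidates. Step 3 is there so that the reported AUCs reflect that risk.
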